≤ Grade 1	Hold dose pending evaluation and observation. Resume with no change in dose when resolved to baseline.
Grade 2	Hold dose pending evaluation and observation. Hold until ≤ grade 1. Patients should go off protocol therapy if treatment with steroids is required. Resume at same dose level for peripheral isolated nerve VII (Bell's palsy).
Grade 3	Off protocol therapy.
Grade 4	Off protocol therapy.
Patients with any CNS events including aseptic meningitis, encephalitis, symptomatic hypophysitis, or myopathy, peripheral demyelinating neuropathy, cranial neuropathy (other than peripheral nerve VII), GB syndrome, or myasthenia gravis should be off study.	
Recommended management: See Neurologic AE Management Algorithm.	

Endocrine Hypophysitis/Adrenal Insufficiency	Management/Next Dose for Nivolumab and Combination Nivolumab/Ipilimumab
≤ Grade 1	Hold pending evaluation, including consultation with an endocrinologist for evidence of adrenal insufficiency or hypophysitis. Patients with asymptomatic TSH elevation may continue treatment while evaluating the need for thyroid replacement.
Grade 2	Hold until patients are on a stable hormone replacement regimen. If treated with steroids, patients must be stable off steroids for 2 weeks. Resume at same dose level.
Grade 3	Hold until patients are on a stable replacement hormone regimen. If treated with steroids, patients must be stable off steroids for 2 weeks. Resume at same dose level.
Grade 4	Off protocol therapy.

Note: All patients with symptomatic pituitary enlargement, exclusive of hormone deficiency, but including severe headache or enlarged pituitary on MRI should be considered grade 3 events. Isolated thyroid or testosterone deficiency may be treated as grade 2 if there are no other associated deficiencies and adrenal function is monitored.
 
Pituitary function should be evaluated before beginning steroid therapy or replacement therapy of any kind.
 
*Note patients with thyroiditis may be retreated on hormone replacement therapy. Patients must be evaluated to rule out pituitary disease prior to initiating hormone replacement therapy.
 
Recommended management: See Endocrine AE Management Algorithm
	

Renal	Management/Next Dose for Nivolumab and Combination Nivolumab/Ipilimumab
≤ Grade 1	See Section 7.2
Grade 2	See Section 7.2
Grade 3	See Section 7.2
Grade 4	See Section 7.2

Infusion Reaction	Management/Next Dose for Nivolumab and Combination Nivolumab/Ipilimumab
≤ Grade 1	See Section 6.9

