Given the heightened risk for cardiac AEs, troponin should be monitored with each dose of nivolumab for the first two months to detect any early evidence of myocarditis. Baseline troponin should be obtained on study, after tacrolimus adjustment. Evaluation of cardiac function, including troponin and CPK levels, EKGs, and echocardiograms as clinically indicated, is recommended for any patients with a history of congestive heart failure or who are at risk because of underlying cardiovascular disease or previous exposure to cardiotoxic drugs.

Note: The optimal treatment regimen for immune mediated myocarditis has not been established. Since this toxicity has caused patient deaths, an aggressive approach is recommended.

All Other Events	Management/Next Dose for Nivolumab and Combination Nivolumab/Ipilimumab
≤ Grade 1	No change in dose.
Grade 2	Hold until ≤ grade 1 or baseline (exceptions as noted below).
Grade 3	Hold until ≤ grade 1 or baseline and patient no longer on steroid treatment, if initiated (exceptions as noted below). Patients should go off protocol therapy for events with a high likelihood of morbidity or mortality with recurrent events.
Grade 4	Off protocol therapy.
Recommended management: As clinically indicated	

Patients requiring high-dose steroid treatment for autoimmune or inflammatory AEs should go off study treatment except for short courses of tapering steroids for infusion reactions, skin rash, or endocrine events.

Patients with grade 3 thyroiditis and skin rash may continue therapy as for grade 2 events with resolution and stable replacement treatment.

Patients with thyroiditis or hypopituitarism who are stable as above may be restarted with replacement hormones including thyroid hormone and physiologic doses of corticosteroids. Please note that hypophysitis with symptoms of headache, visual or neurologic changes, or radiologic evidence of pituitary enlargement and other CNS events such as aseptic meningitis or encephalitis should be considered grade 3 events.

Prior to starting corticosteroids or hormone replacement for any reason, appropriate endocrine testing, including cortisol, adrenocorticotrophic hormone (ACTH), TSH, and T4, must be obtained to document baseline.

Please note that in some cases the treatment algorithms recommend steroids if symptoms do not resolve in 7 days. However, this recommendation is not meant to delay steroid treatment at any time it is clinically indicated.

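### Section 7.1 both stops and resumes therapy after Grade 3 symptomatic hypophysitis with pituitary enlargement or severe headache, and no visible rule says which applies

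*Combined protocol and SAP*

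**What the plan says.** All the text is in Section 7.1, which asks sites to use its tables as written.

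- **Neurologic Events table.** The Grade 3 row ends protocol therapy. The note below it begins "Patients with any CNS events including aseptic meningitis, encephalitis, symptomatic hypophysitis, or myopathy, peripheral demyelinating neuropathy" and ends "cranial neuropathy (other than peripheral nerve VII), GB syndrome, or myasthenia gravis should be off study". It sets no grade limit.
- **Endocrine Hypophysitis/Adrenal Insufficiency table.** At Grade 3, drug is held until the patient is on a "stable replacement hormone regimen. If treated with steroids, patients must be stable off steroids for 2 weeks. Resume at same dose level". Only Grade 4 ends therapy.
- **Note under the Endocrine table.** "All patients with symptomatic pituitary enlargement, exclusive of hormone deficiency, but including severe headache or enlarged pituitary on MRI" are to be treated as Grade 3.
- **Closing text, after the All Other Events table.** It allows some restarts: "Patients with thyroiditis or hypopituitarism who are stable as above may be restarted with replacement hormones including thyroid hormone". It then grades pituitary events: "Please note that hypophysitis with symptoms of headache, visual or neurologic changes, or radiologic evidence of pituitary enlargement", with the sentence ending "or radiologic evidence of pituitary enlargement and other CNS events such as aseptic meningitis or encephalitis should be considered grade 3 events". It also names Grade 3 exceptions: "Patients with grade 3 thyroiditis and skin rash may continue therapy as for grade 2 events". Hypophysitis is not among them.

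**The concern.** Two adjacent tables claim the same Grade 3 event and give outcomes that cannot both be followed. One ends dosing; the other restarts it at the same dose once the hold conditions are met. Section 6.3 applies the Section 7 guidance to the combination as well, so re-exposure could be to nivolumab alone or with ipilimumab. In a multi-institution trial, two sites that each follow the tables could manage the same event in opposite ways. What is at stake is consistent safety management of a few patients, not the trial's error rates or power.

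**Working it through.** No arithmetic applies; the check sets the rules side by side.

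**Step 1: grade one patient.** Take hypophysitis with an enlarged pituitary and severe headache. The Endocrine note makes it Grade 3. The closing text also makes hypophysitis with headache, or with radiologic enlargement, Grade 3. The grade is not in dispute.

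**Step 2: read off the outcome in each table.**

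| Grade | Neurologic table and note | Endocrine table | Result |
|---|---|---|---|
| 1 or below | Row: hold, resume at baseline | Hold pending evaluation | No practical conflict: enlargement or severe headache is lifted to Grade 3 |
| 2 | Row: hold, stop if steroids are needed; note is ungraded | Hold, then resume | Narrow overlap, mainly symptoms of hormone deficiency |
| 3 | Row: off protocol therapy; note: off study | Hold, then resume at same dose | Incompatible |
| 4 | Off protocol therapy | Off protocol therapy | Agree |

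The clear conflict is in one of the four endocrine rows.

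**Step 3: separate the presentations.** Enlargement and severe headache are graded 3 in both places. Visual and neurologic changes are graded 3 only in the closing text. That text puts them alongside other CNS events, which favours stopping.

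**Step 4: look for a rule that decides.**

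- The note opening Section 7 covers a patient with several adverse events and picks the most severe. Here one event at one grade sits in two tables.
- The (#) mark in Section 7.1 flags differences between the tables and the Appendix B algorithms. Neither hypophysitis entry carries it, and it does not rank one table over another.
- The high-dose steroid rule exempts short tapering courses for endocrine events, so it does not force a stop.
- The Endocrine note's exclusion of hormone deficiency does not move mass-effect cases elsewhere. The note sits under the Endocrine table and assigns them Grade 3 there.
- The investigator-judgment rule permits a stop but does not say which row is the default.

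**Step 5: compare with other tables.** Where Section 7.1 wants a split outcome, it writes one in. The Pancreatitis Grade 3 row sends symptomatic pancreatitis off therapy, and the Cardiac table separates suspected from confirmed myocarditis. The Endocrine Grade 3 row has no such split.

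**The case against.** The strongest reply is that the text nearly resolves itself. The Neurologic note names symptomatic hypophysitis and gives one outcome. The Endocrine hold condition is stable hormone replacement, which suits deficiency and fits poorly with enlargement that excludes deficiency. The closing text lets stable hypopituitarism restart and then groups symptomatic hypophysitis with meningitis and encephalitis. It also omits hypophysitis from its named Grade 3 exceptions. Read together, deficiency resumes and mass effect stops. This reading is plausible and probably intended. What it lacks is any sentence that limits the Endocrine Grade 3 row to deficiency.

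A second reply is that the Appendix B algorithms are to be followed, and their endocrine and neurological figures are not visible in the text available here. That stands as a reason for moderate rather than high confidence. Section 7.1 does not, however, make the algorithms a tie-break between its own tables, and each table refers to a different algorithm.

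A third reply is that oversight limits the harm. Section 7.1 takes off therapy any patient whose event the investigator judges a substantial clinical risk, and it recommends consulting the study PI or drug monitor. Section 13.1 adds at least monthly calls with the CTEP Medical Officer. This stands and lowers the priority.

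A reader might also infer that pituitary enlargement seen only on MRI, without symptoms, is caught in the same conflict. The documents do not clearly support that. The Neurologic note is limited to symptomatic hypophysitis, which leaves the Endocrine Grade 3 row as the specific instruction.

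**Conclusion.** The inconsistency is real for symptomatic hypophysitis with pituitary enlargement or severe headache at Grade 3. It rests on the visible text of Sections 7 and 7.1. Confidence is moderate because the Appendix B figures could not be read, and priority is low to moderate.

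Three stronger readings are tempting, and the documents do not support them.

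- **That sites must re-dose patients at risk.** They need not: the investigator stop rule is always available.
- **That the efficacy results are affected.** None of this is shown. Section 6.2 assesses week 16 regardless of doses received, Section 6.8 keeps patients stopped for drug toxicity in follow-up, and Section 9.5 analyses PFS and OS in everyone dosed.
- **That the number of affected patients can be read from the adverse event lists in Section 10.1.** Those frequency bands cover hypophysitis of any kind. The documents give no rate for the symptomatic Grade 3 form. The only firm bound is enrolment, between 9 and 16 patients (Section 9.2).

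**What to change.** State one outcome for the event. The version closer to the existing text has three edits:

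1. In the Endocrine Grade 3 row, say that hypophysitis with headache, visual or neurologic symptoms goes off protocol therapy per the Neurologic table.
2. In the same row, limit hold-and-resume to hormone deficiency that is stable on replacement.
3. In the Neurologic note, replace *off study* with *off protocol therapy*. This matches the table rows and the follow-up that Section 6.8 provides after drug toxicity; Section 6.7 already records stopping therapy and leaving the study separately.

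If the sponsor intends resumption instead, delete symptomatic hypophysitis from the Neurologic note and separate it from the other CNS events in the closing text.

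Either version is a short text amendment with no new visits or data, though choosing between them is a clinical decision for the sponsor. The first has a real cost: a few patients may lose the chance to resume, in a population enrolled because standard therapy would be insufficient.

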7.2 Prednisone and Tacrolimus Dose Modifications for Allograft Rejection

Given the potential for rejection due to the administration of nivolumab and ipilimumab in this study, patients should be monitored closely for signs of rejection.

Markers of allograft rejection may include the following:

- Unexplained $\geq 20\%$ increase in serum creatinine over baseline,
- Development of donor-specific antigen (DSA) or non-HLA antibodies,
- Development of severe proteinuria (>1 g/day),
- Persistent increase in dd-cfDNA.

Serum creatinine (included in the comprehensive metabolic panel) will be monitored according to the schedule outlined in the treatment calendars (Section 11).

Donor-specific and non-HLA antibodies should be checked as clinically indicated at the direction of the institution's transplant nephrologist. Patients should be encouraged to report possible symptoms of rejection, including elevated temperature, elevated blood pressure, graft tenderness, and blood in the urine. Although experimental in this setting, dd-cfDNA levels (see Section 2.5.3 and the Biomarker Plan, Section 5.6) may be useful to monitor for signs of rejection.

Dipstick urinalysis should be performed per the schedule outlined in the treatment calendars. If 2+ or greater, a urine protein/creatinine ratio (spot or 24-hour) should be assessed at the direction of the institution's transplant nephrologist.

If rejection is suspected based on the above analyses, the following interventions will be triggered:

1. Hold or discontinue nivolumab (and ipilimumab, if applicable)
2. Immediately biopsy the renal allograft
 - a. If cell-mediated rejection: Increase the tacrolimus dose (target trough level = 5-10 ng/mL) and administer 500 mg IV methylprednisolone daily for 3 days, with a prednisone taper thereafter. If no improvement, administer 5 mg/kg infliximab.
 - b. If antibody-mediated rejection: Increase the tacrolimus dose (target trough level = 5-10 ng/mL), perform plasmapheresis, and administer IV immunoglobulin (Ig) per institutional protocol plus 500 mg IV methylprednisolone daily for 3 days with a prednisone taper thereafter.

A patient who experiences clinical benefit from the above regimen and still has a functional kidney allograft may restart study therapy after re-screening and consultation with the PI if the patient:

- Experienced an objective response or SD on study therapy,
- Experiences progressive or recurrent disease after having been off study therapy, and
- Has been off study therapy for at least 90 days, but less than 1 year.

Patients who experience allograft loss should begin dialysis and may resume nivolumab monotherapy or nivolumab plus ipilimumab combination therapy, as appropriate.

Dose modifications of tacrolimus and prednisone should be done per standard of care.

8. PHARMACEUTICAL INFORMATION

A list of the adverse events and potential risks associated with the investigational and commercial agents administered in this study can be found in Section 10.1.

8.1 CTEP IND Agent(s)

8.1.1 Nivolumab (NSC 748726)

Amino Acid Sequence: 4 polypeptide chains, which include 2 identical heavy chains with 440 amino acids and 2 identical light chains.

Other Names: nivolumab, MDX1106

Classification: Anti-PD-1 MAb

M.W.: 146,221 Daltons

Mode of Action: Nivolumab targets the PD-1, CD279 cell surface membrane receptor. PD-1 is a negative regulatory receptor expressed by activated T and B lymphocytes. Binding of PD-1 to its ligands, PD-L1 and 2 PD-L2, results in the down-regulation of lymphocyte activation. Nivolumab inhibits the binding of PD-1 to PD-L1 and PD-L2. Inhibition of the interaction between PD-1 and its ligands promotes immune responses and antigen-specific T-cell responses to both foreign antigens as well as self-antigens.

Description: Nivolumab Injection is a clear to opalescent, colorless to pale yellow liquid; light (few) particulates may be present. The drug product is a sterile, nonpyrogenic, single-use, isotonic aqueous solution formulated in sodium citrate, sodium chloride, mannitol, diethylenetriaminepentacetic acid (pentetic acid), polysorbate 80 (Tween™ 80), and water for injection. Dilute solutions of hydrochloric acid and/or sodium hydroxide may be used for pH adjustment (pH 5.5-6.5).

How Supplied: Nivolumab is supplied by Bristol-Myers Squibb and distributed by the Pharmaceutical Management Branch (PMB), CTEP/DCTD/NCI as 100 mg vials (10 mg/mL) with a 0.7 mL overfill. It is supplied in 10 mL type I flint glass vials, with fluoropolymer film-laminated rubber stoppers and aluminum seals.

Preparation: Nivolumab injection can be infused undiluted (10 mg/mL) or diluted with 0.9% Sodium Chloride Injection, USP or 5% Dextrose. When the dose is based on patient weight (*i.e.*, mg/kg), nivolumab injection can be infused undiluted or diluted to protein concentrations as low as 0.35 mg/mL. When the dose is fixed (*e.g.*, 240 mg, 360 mg, or 480 mg flat dose), nivolumab injection can be infused undiluted or diluted so as not to exceed a total infusion volume of 160 mL. For patients weighing less than 40 kg, the total volume of infusion must not exceed 4 mL per kg of patient weight. During drug product preparation and handling, vigorous mixing or shaking is to be avoided.

Nivolumab infusions are compatible with polyvinyl chloride (PVC) or polyolefin containers and infusion sets, and glass bottles.

Storage: Vials of Nivolumab injection must be stored at 2-8 °C (36-46 °F) and protected from light and freezing. The unopened vials can be stored at room temperature (up to 25 °C, 77 °F) and room light for up to 48 hours.

If a storage temperature excursion is identified, promptly return Nivolumab to 2-8 °C and quarantine the supplies. Provide a detailed report of the excursion (including documentation of temperature monitoring and duration of the excursion) to [contact] for determination of suitability.

Stability: Shelf-life surveillance of the intact vials is ongoing.

The administration of undiluted and diluted solutions of Nivolumab must be completed within 24 hours of preparation. If not used immediately, the infusion solution may be stored up to 24 hours at 2-8 °C (36-46 °F) and a maximum of 8 hours of the total 24 hours can be at room temperature (20-25 °C, 68-77 °F) and room light. The maximum 8-hour period under room temperature and room light conditions includes the product administration period.

CAUTION: The single-use dosage form contains no antibacterial preservative or bacteriostatic agent. Therefore, it is advised that the product be discarded 8 hours after initial entry.

Route of Administration: Intravenous infusion over 30 minutes. Do not administer as an IV push or bolus injection.

Method of Administration: Administer through a 0.2-1.2-micron pore size, low-protein binding (polyethersulfone membrane) in-line filter.

Potential Drug Interactions: The indirect drug-drug interaction potential of nivolumab was assessed using systemic cytokine modulation data for cytokines known to modulate CYP enzymes. There were no meaningful changes in cytokines known to have indirect effects on CYP enzymes across all dose levels of nivolumab. This lack of cytokine modulation suggests that nivolumab has no or low potential for modulating CYP enzymes, thereby indicating a low risk of therapeutic protein-drug interaction.

Patient Care Implications: Women of childbearing potential (WOCBP) receiving nivolumab must continue contraception for a period of 5 months after the last dose of nivolumab. Men receiving nivolumab and who are sexually active with WOCBP must continue contraception for a period of 7 months after the last dose of nivolumab.

Availability: Nivolumab is an investigational agent supplied to investigators by the Division of Cancer Treatment and Diagnosis (DCTD), NCI. Nivolumab is provided to the NCI under a Collaborative Agreement between Bristol-Myers Squibb and the DCTD, NCI (see Section 13.4).

8.1.2 Ipilimumab

Chemical Name or Amino Acid Sequence: 4 polypeptide chains, 2 identical heavy chains with 447 amino acids and 2 identical light chains consisting of 215 amino acids.

Other Names: Anti-CTLA-4 monoclonal antibody, MDX-010, Yervoy™

Classification: Human monoclonal antibody

M.W.: 147,991 Daltons

Mode of Action: Ipilimumab is specific for the CTLA4 antigen expressed on a subset of activated T-cells. CTLA4 interaction with the B7 molecule, one of its ligands expressed on professional antigen presenting cells, can down-regulate T-cell response. Ipilimumab is thought to act by blocking the interaction of CTLA4 with the B7 ligand, resulting in a blockade of the inhibitory effect of T-cell activation.

Description: Ipilimumab is a fully human immunoglobulin (IgG₁K) with two manufacturing processes – ongoing trials have been using substances manufactured using Process B. New clinical trials will be using ipilimumab that is manufactured by Process C. The Process C has been developed using a higher producing sub-clone of the current Master Cell Bank, and modified cell culture and purification steps.

How Supplied: Ipilimumab is supplied by Bristol-Myers Squibb and distributed by the PMB, CTEP/DCTD/NCI. Ipilimumab for injection, 200 mg/40 mL (5 mg/mL), is formulated as a clear to slightly opalescent, colorless to pale yellow, sterile, nonpyrogenic, single-use, isotonic aqueous solution that may contain particles.

Each vial is a Type I flint glass vial with gray butyl stoppers and sealed with aluminum seals.

Component	Process C
Ipilimumab	200 mg/ vial^a
Sodium Chloride, USP	213 mg
TRIS-hydrochloride	249 mg
Diethylenetriamine pentacetic acid	134.3 mg
Mannitol, USP	1.67 mg
Polysorbate 80 (plant-derived)	426 mg
Sodium Hydroxide	4.69 mg
Hydrochloric acid	QS to pH 7
Water for Injection	QS to pH 7
Nitrogen ^b	QS: 42.6 mL
	Processing agent

^aIncludes 2.6 mL overfill.

^bNitrogen is used to transfer the bulk solution through the pre-filled and sterilizing filters into the aseptic area.

Preparation: Ipilimumab is given undiluted or further diluted in 0.9% NaCl Injection, USP or 5% Dextrose Injection, USP in concentrations between 1 mg/mL and 4 mg/mL. Ipilimumab is stable in a polyvinyl chloride (PVC), non-PVC/non DEHP (di-(2-ethylhexyl) phthalate) IV bag or glass container up to 24 hours refrigerated at 2-8 °C (36-46 °F) or at room temperature/ room light.

Recommended safety measures for preparation and handling include protective clothing, gloves, and safety cabinets.

Storage: Store intact vials refrigerated at 2-8 °C (36-46 °F), protected from light. Do not freeze.

Stability: Shelf-life surveillance of the intact vials is ongoing. Solution as described above is stable up to 24 hours refrigerated at 2-8 °C (36-46 °F) or at room temperature/ room light.

CAUTION: Ipilimumab does not contain antibacterial preservatives. Use prepared IV solution immediately. Discard partially used vials.

Route of Administration: Intravenous infusion over 30 minutes. Do not administer ipilimumab as an IV push or bolus injection.

Method of Administration: Can use a volumetric pump to infuse ipilimumab at the protocol-specific dose and rate via a PVC IV infusion set with an in-line, sterile, non-pyrogenic, low-protein-binding filter (0.2-1.2 micron).

Patient Care Implications: Monitor patients for immune-related adverse events, *e.g.*, rash/vitiligo, diarrhea/colitis, uveitis/episcleritis, hepatitis and hypothyroidism.

